- **Appendix D. Activity table:** Adjust eDiary data review process to remove review of eCOA eligibility report and include eDiary data manual review for subject eligibility.
- **Operations Manual - Section 1 Contacts:** contacts updated to reflect current roles.
- **Operations Manual – throughout as applicable:** adjust eDiary review to include manual review for eligibility.
- **Operations Manual – Section 3 Rescue Medication:** add rescue medication records clarification to be recorded in the EDC and eDiary.
- **Operations Manual – Section 3.8 Optional Pharmacokinetic Sampling:** clarify blood should be collected from a vein. Blood collected from heel, finger or ear stick may contain interstitial/tissue fluid and therefore is not acceptable.
- **Operations Manual – Section 4.2 Reporting Adverse Events and Intercurrent Illnesses:** Update emergency medical contact to [name].
- **Operations Manual – Appendix B Acceptable Protocol Modifications:** update to specify unforeseen circumstances and clarify what protocol activities can be modified.

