3.3 Rescue Medications

Refer to Table 2 of Protocol Section 5.3 for the protocol-permitted rescue medications. Of note,

- Any laxatives are to be discontinued prior to the Preintervention Visit in favor of the site-supplied, protocol-permitted rescue medications.
- Rescue medication is not to be used on the calendar day before enrollment/randomization (Visit 3) and on the day of the enrollment/randomization Visit (Visit 3) until randomization/enrollment.
- Rescue medication (name of medication, dose, and route of administration) records will include medication given by the caregiver/parent/guardian/LAR as well as information from secondary caregivers if the participant was in the care of others. Rescue medication is recorded in the EDC and the eDiary.
- Rescue medication may be taken when at least 72 hours have passed since the subject's previous BM or when their symptoms become intolerable.

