3.7 Observer-Reported Outcomes

An observer-reported outcome (ObsRO) eDiary instrument assessing key signs and symptoms of FC for use in children (6 months to 5 years of age) with FC was developed by AbbVie and Ironwood Pharmaceuticals based on extensive qualitative research with LAR/parent/guardian/caregivers of children with FC, as well as feedback from pediatric gastroenterologists, measurement experts, and health authorities. The ObsRO instrument was developed for completion by LAR/parent/guardian/caregivers on an electronic diary (eDiary) and is being employed in this study for

use in subjects 6 months to less than 2 years of age. Data collected in the eDiary will be used to derive the efficacy endpoints.

All efficacy assessments will be determined by responses entered in the eDiary by the LAR/parent/guardian/caregiver. The LAR/parent/guardian/caregiver is identified as the individual who completes the eDiary and should be the same individual throughout the course of the study and must be able to read and understand the eDiary as a condition for study participation (inclusion criterion). At the start of the Preintervention Period, LAR/parent/guardian/caregivers will receive full training on the use and completion of the eDiary at the study visit in which they are given the eDiary device. If the LAR/parent/guardian/caregiver completing the diary changes, the study team should be notified and should document the date when it changed and who the new LAR/parent/guardian/caregiver is. The new LAR/parent/guardian/caregiver must also provide written informed consent before the initiation of any study-specific procedures.

The key efficacy assessments, which will be used to determine the efficacy parameter of SBM frequency, are the items assessing BM frequency and rescue medication use in the daily eDiary, once a day in the evening.

Assessments of global change in symptoms and global severity of symptoms will be completed weekly in the eDiary. The global assessments consist of 2 items; 1 assessing global change in the child's symptoms and 1 assessing the global severity of the child's symptoms. Both global items will be completed weekly on the eDiary by the LAR/parent/guardian/caregiver. The global severity item will be completed beginning at the Preintervention Period through the 1-week post intervention visit.

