Appendix B. Variable Derivation

Missed eDiary Assessments

No imputation or derivation will be performed for missed eDiary assessments unless otherwise specified.

Incomplete eDiary Assessments

Missing responses in incomplete eDiary assessments will not be imputed for most of the parameters, with the exception of rescue medication (RM) use and BM frequency.

If the answer to the RM use question is missing in eDiary, no RM usage will be considered during that diary period in eDiary.

If the answer to the question related to BM frequency is missing in any daily eDiary, BM frequency will be considered as zero for that diary period in the eDiary.

Incomplete Clinic Diary on Enrollment/Randomization Visit

Missing responses in an incomplete clinic diary on enrollment/randomization day will be handled in a similar way as mentioned for incomplete daily eDiary assessments.

Stool frequency

Spontaneous Bowel Movement (SBM)

A SBM is a BM that occurs in the absence of laxative, suppository, or enema use on the calendar day of the BM or the calendar day before the BM.

Stool Frequency Rates

The components for calculating a subject's stool frequency rates (SBM weekly rates) for a given period are as follows:

- The number of BMs that occurred during that specific period

- The number of those BMs that were SBMs
- The number of days during that specific period:
- Enrollment/Randomization day will be considered as a half day for the double-blind intervention period and preintervention period.

Duration of an Analysis Week

With respect to a subject's scheduled analysis weeks, the term duration is used. In regard to the duration of a week, it is expected that 1 or more of a subject's "weeks" may not be exactly 7 days in duration (e.g., a subject may withdraw or discontinue early from the trial or may have missing diary day). Deviations from the 7 days norm are structural in nature; and, as such, the calculations of the weekly rates of SBMs will incorporate the actual days contributed within the time period (week or specific phase).

Weekly Stool Frequency Rate Calculations

The weekly frequency rate for SBMs will be based on the total number of SBMs reported by a caregiver as being directly observed by the caregiver based on the diary entries during that time period, adjusting for differences in the length of the time period. Weekly stool frequency rates for each specific period will be calculated as follows:

Weekly Frequency Rate (Specific Period) =

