$$\frac{\text{Total number of directly observed SBMs reported by a caregiver during the specific period}}{\text{Number of days during the specific period}} * 7$$

The weekly frequency rate for SBMs will also be derived based on the total number of SBMs occurring based on the diary entries during that time period (including SBMs not directly observed by the caregiver), adjusting for differences in the length of the time period.

Weekly Frequency Rate (Specific Period) including SBMs not directly observed by caregiver =

$$\frac{\text{Total number of SBMs during the specific period}}{\text{Number of days during the specific period}} * 7$$

Stool Consistency

The caregiver will be asked to rate the child's observed stool consistency for each BM the caregiver was present for using the Bristol Stool Form Scale (BSFS), a 7-point ordinal scale:

"Choose the option that is most like bowel movement X you were with the child for"

Type 1: Separate hard lumps, like nuts

Type 2: Sausage-shaped but lumpy

Type 3: Like a sausage, but with cracks on the surface

Type 4: Like a sausage or snake, smooth and soft

Type 5: Soft blobs with clear cut edges

Type 6: Fluffy pieces with ragged edges, a mushy stool

Type 7: Watery, no solid pieces.

I don't know.

A subject's stool consistency score for the study intervention period will be the average of the non-missing BSFS scores for the caregiver-observed SBMs during that specific period.

Straining

If the caregiver was present for the BM, the caregiver will be asked to rate the amount of straining observed when the child passed the BM using the following two 3-point rating scales. The caregiver will be asked to assess the degree of straining for every BM for which he/she was present by responding to the following two questions in the daily eDiary:

For the bowel movement X you were with the child for, did he/she grunt like he/she was straining?

- No, not at all
- Yes, a little
- Yes, a lot
- I don't know

For the bowel movement X you were with the child for, did he/she make a face like he/she was straining?

- No, not at all
- Yes, a little
- Yes, a lot
- I don't know

The subject's daily straining score for each caregiver-observed BM will be derived based on the average of non-missing responses of the two straining questions. The subject's straining score will be the average of the non-missing daily average straining scores for the caregiver-observed SBMs during the specific period.

Global Items

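### A blank eDiary rescue item is scored as no rescue, with no role for the EDC rescue record, so a rescue-related BM can count as spontaneous

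*SAP*

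**What the plan says.** SAP Appendix B, under incomplete eDiary assessments, makes two exceptions to its policy of not imputing. For rescue medication: "If the answer to the RM use question is missing in eDiary, no RM usage will be considered during that diary period in eDiary". For a blank BM item: "BM frequency will be considered as zero for that diary period in the eDiary". An incomplete clinic diary on the enrollment/randomization day is handled in a similar way.

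Operations Manual 3.3 (in the protocol document) says: "Rescue medication is recorded in the EDC and the eDiary". It adds that these records include information from secondary caregivers. Protocol Appendix F lists the change as "add rescue medication records clarification to be recorded in the EDC and eDiary".

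Protocol 7.3 and SAP 8.0 say that a BM is not an SBM if a laxative, enema or suppository was taken on the same calendar day or the day before. Neither names a data source. Operations Manual 3.7 does: "All efficacy assessments will be determined by responses entered in the eDiary". It lists the daily BM and rescue items as the basis for SBM frequency.

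The SAP does not mention the EDC rescue record. SAP 14.1 declares no change from the protocol's planned analyses.

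**The concern.** The SBM rate is the first key efficacy endpoint, and whether a BM is spontaneous depends entirely on rescue use. If the eDiary item is blank and the EDC shows rescue, the trial knows that the BM was not spontaneous, yet Appendix B scores it as if no rescue had been taken. The error goes one way: a blank rescue item can only raise an SBM rate. At baseline that shrinks the change score; on treatment it enlarges it.

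A caregiver-observed BM that is wrongly classed as spontaneous also enters the consistency and straining averages (SAP 9.3.1), so all three key endpoints are exposed.

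Rescue use is foreseeable. Entry requires an average of two or fewer SBMs per week, that is, a mean spacing of at least 168/2 = 84 hours, and rescue is permitted once 72 hours have passed since the last BM. The comparison is only indicative, because the 72 hours run from any BM and not from the last SBM.

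**Working it through.** The plan gives no figure to reproduce: the study is descriptive and states no rescue or blank-item counts. The check uses the SAP's own rate formula with assumed counts.

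**Inputs**
- Rate = directly observed SBMs ÷ days × 7, where days means "Number of days during the specific period" (SAP Appendix B).
- Baseline window: 14 days before enrollment up to the time of enrollment (SAP 9.1). Intervention: 28 days.
- Half-day rule: "Enrollment/Randomization day will be considered as a half day for the double-blind intervention period and preintervention period".
- Six subjects per Part 1 cohort, and 12 randomized 1:1 in Part 2, so six per arm.

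**Days**
- Baseline: 14 + 0.5 = 14.5.
- Treatment: 28 − 0.5 = 27.5. The half-day rule does not name the open-label period, so 28 is also tried.

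**One rescue-related, observed BM counted as spontaneous**
- Baseline: 7/14.5 = 0.48 per week.
- Treatment: 7/27.5 = 0.25 per week (7/28 = 0.25).
- Mean of six: 0.483/6 = 0.08 and 0.255/6 = 0.04.

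**Two such BMs in one child**
- Baseline: 14/14.5 = 0.97. Treatment: 14/27.5 = 0.51.

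**Effect on that child's change score**
- Baseline event only: −0.48. Treatment event only: +0.25. One in each period: 0.255 − 0.483 = −0.23. The net direction depends on where the blanks fall.

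**The blank-BM rule, for comparison**
A wholly missed diary shortens the period; Appendix B recognizes that "a subject may withdraw or discontinue early from the trial or may have missing diary day". A blank BM item in a submitted diary is scored as zero and, on the natural reading, its day stays in the denominator. With four blank days on treatment:
- If those days had BMs at the child's average rate, the zero rule turns 4.0 into 4.0 × 23.5/27.5 = 3.42.
- If they truly had none, dropping the days turns 16 × 7/27.5 = 4.07 into 16 × 7/23.5 = 4.77.

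Each rule is wrong by the same ratio (27.5/23.5 = 1.17) when the other's assumption holds.

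**Table 1 wording**
SAP Table 1 says that data from the rescue day and the next day are not used, whereas SAP 8.0 and Appendix B only reclassify the BMs. With 8 SBMs, keeping the days gives 8 × 7/27.5 = 2.04. Removing two days per use, for 1, 2 or 4 non-overlapping uses, gives 8 × 7/25.5 = 2.20, 8 × 7/23.5 = 2.38 or 8 × 7/19.5 = 2.87.

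**The case against.** The strongest reply is that the SAP is silent on the EDC and does not forbid it. The rescue rule confines itself to the eDiary, and Operations Manual 3.7 names the eDiary as the efficacy source, so Appendix B follows current protocol text. That stands as far as it goes: this is an unreconciled gap, and the fix has to address 3.7 openly. It does not remove the problem, because the endpoint rule turns on actual use and a second record of use exists.

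The error also needs a coincidence: real rescue use, a blank item, and a BM that day or the next. The documents do not say whether the device allows skipped items, although Appendix B provides for incomplete diaries. The SAP 6.3 compliance summary will show how often diaries are not fully completed, but not which item was blank.

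A reader might infer more than the documents support:
- *That EDC recording was introduced after the SAP (17 May 2023) and the SAP is out of date.* Appendix F of the current protocol (25 November 2024) calls it a clarification, which does not show that the practice was new.
- *That the zero rule for a blank BM item is an error or contradicts SAP 9.2.* It is an express, prespecified exception, and its replacement errs by the same ratio the other way. Section 9.2 lacks only a cross-reference.
- *That Table 1 changes the main result.* SAP 3.1 and 9.1 send the derivation to Appendix B, and Table 1 uses the same sentence for consistency and straining, which have no day denominator. Appendix B most likely governs.
- *That dose selection would be distorted.* The documents do not say that the dose escalation committee works from these derived rates.

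**Conclusion.** The concern holds for the rescue item. As written, the SAP can count as spontaneous a BM that the trial's own database shows to be rescue-related, and no rule reconciles the two sources. Under an assumed single event the effect is modest: about 0.48 per week at baseline or 0.25 on treatment in one child, and 0.08 or 0.04 in a six-subject mean. It grows in proportion to the number of such events, which is unknown. No test is performed, so no error rate is at stake; what is at stake is avoidable bias in small descriptive means. The blank-BM rule and the Table 1 wording are minor, and neither is grounds for changing the main analysis.

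**What to change.** In SAP Appendix B:
1. When the eDiary rescue item is blank, use the dated EDC rescue record, and assume no rescue only if the EDC also shows none.
2. State how an eDiary answer of no against an EDC entry of rescue use is resolved, since that is the same misclassification.
3. Reconcile the rule with Operations Manual 3.7 in one sentence, and declare it in SAP 14.1.
4. Tabulate days with a blank rescue item or a blank BM item, by period.

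The cost is SAP wording, one merge of EDC rescue data and a few table rows. No study procedure changes. There is one dependency. Operations Manual 3.3 lists medication name, dose and route but not date, and the SBM rule needs the calendar day. The sponsor must confirm that the EDC holds the date of use; if it does not, only the tabulation is possible.

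Optional and minor: keep the zero rule for a blank BM item as the main analysis and add a sensitivity analysis that excludes those days; align the Table 1 rescue-day wording with SAP 8.0 and Appendix B, which leaves the main result unchanged; and cross-refer to the Appendix B exceptions in SAP 9.2.

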In each cohort of Part 1, at least 1 subject will need to be \leq 12 months of age. The study investigator and the LAR/parent/guardian will be given the option for the subject to continue in the next higher cohort (dose escalation) if the safety profile favors a trial cohort at a higher dose. In Part 1, new subjects will be recruited for each cohort, but existing subjects from previous cohorts (Cohorts 1 and 2) will be given the opportunity to participate in the next cohort (up to Cohort 3) if their symptoms have not improved at that respective dose (\leq 2 SBM per week), the subject has an acceptable tolerability to the study drug, and the LAR/parent/guardian is willing to continue in the study.

Subjects who are participating in intrasubject dose escalation will need to repeat all screening procedures and eDiaries if $>$ 30 days have elapsed since the subject's last dose in the previous cohort. Note: the screening number assigned by the Interactive response technology (IRT) at the initial screening visit should still be used. If symptoms have improved at the current dose level, the subject will be invited to participate in a long-term safety extension study, once the study is active and accepting subjects. An internal Dose Escalation Review Committee will be monitoring the safety of Cohorts 1-3 and will provide a recommendation for the dose escalation to the next cohort or to stop the study based on the overall benefit-risk profile. The dose will be selected based on: 1) the absence of treatment-related AESI within the cohort and 2) an increase in SBM frequency per week compared to baseline with or without improvement of at least 1 point in the Bristol Stool Form Scale (BSFS) scale. The minimum effective dose will be selected.

Once the best benefit-risk dosing profile from Cohorts 1-3 has been identified, Part 2 (the final cohort) will include 12 subjects at 4 weeks of double-blind study intervention with linaclotide vs. placebo using that selected dose. An independent DSMB will review unblinded interim safety data for that cohort. Based on this review, the DSMB will assess the overall safety of the subjects in Part 2.

In Part 2, new subjects will be recruited. Data based on the final selected dose will be analyzed and compared with a placebo. Similarly, safety and efficacy will be analyzed across all cohorts (Parts 1 and 2) and to placebo. Those results will be used to support the feasibility of a confirmatory Phase 3 study.

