2.3 Treatment Assignment and Blinding

Approximately 30 subjects, 6 months to less than 2 years of age, will be sequentially enrolled into this study: six subjects in each cohort for Cohorts 1-3 and twelve subjects for

Part 2. Cohorts 1 to 3 will be open label with linaclotide only. Part 2 will be double blinded, and subjects will be randomized at a 1:1 ratio to linaclotide or placebo.

All cohorts will be of 7 to 12 weeks in duration: 0 to 4-week Screening Period (the minimal of 0 to 4-week period only applies to subjects that need wash out from prohibited medications), a 2 to 3-week Preintervention Period, followed by a 4-week Study Intervention Period, and a 1-week Postintervention Period.

In Part 1, linaclotide will be administered orally QD at the dose of 9 µg, 18 µg, and 36 µg for Cohort 1, Cohort 2 and Cohort 3, respectively. Part 2 will include additional subjects at the dose of linaclotide (either the 9, 18, or 36 µg dose) that exhibited the best benefit-risk profile from Part 1; and subjects receiving matching placebo.

In Cohorts 1-3, at least 5 subjects per cohort will need to complete treatment with an acceptable safety profile assessed by an internal Dose Escalation Review Committee which will give special attention to the presence of AESIs for the cohort to be declared safe to escalate to the next dose level.

In each cohort of Part 1, at least 1 subject will need to be \leq 12 months of age. The study investigator and the legally authorized representative (LAR)/parent/guardian will be given the option for the subject to continue in the next higher cohort (dose escalation) if the safety profile favors a trial cohort at a higher dose. Subjects who are participating in intrasubject dose escalation will need to repeat all screening procedures and eDiaries if > 30 days have elapsed since the subject's last dose in the previous cohort. Note: the screening number assigned by the Interactive response technology (IRT) at the initial screening visit should still be used. If symptoms have improved at the current dose level, the subject will be invited to participate in a long-term safety extension study once the study is active and accepting subjects. An internal Dose Escalation Review Committee will be monitoring the safety of Cohorts 1-3 and will provide a recommendation for the dose escalation to the next cohort or to stop the study based on the overall benefit-risk profile.

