Once the best benefit-risk dosing profile from Cohorts 1-3 has been identified, Part 2 (the final cohort) will include 12 subjects at 4 weeks of double-blind study intervention with linaclotide vs. placebo using that selected dose. An independent Data Safety Monitoring Board (DSMB) will review unblinded interim safety data for that cohort. Based on this review, the DSMB will assess the overall safety of the subjects in Part 2.

In Part 1, new subjects will be recruited for each cohort, but existing subjects from previous cohorts (Cohorts 1 and 2) will be given the opportunity to participate in the next cohort (up to Cohort 3) if their symptoms have not improved at that respective dose (≤ 2 SBM per week), the subject has an acceptable tolerability to the study drug, and the LAR/parent/guardian is willing to continue in the study.

In Part 2, new subjects will be recruited. The final selected dose will be analyzed and compared to placebo. Similarly, safety and efficacy will be analyzed across all cohorts (Parts 1 and 2) and to placebo. Those results will be used to support the feasibility of a confirmatory Phase 3 study.

The Phase 2 open-label ascending, multidose dose finding portion of the study (Part 1) will provide a safe and efficient method of identifying a suitable dose to assess in Part 2 of the study, where blinding to randomized controlled treatment can then be employed to provide more confidence on the safety and efficacy of linaclotide in this young pediatric population and to support further research in a Phase 3 study.

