3.0 Endpoints

3.1 Key Efficacy Endpoints for Part 1 and Part 2

The key efficacy endpoints for Part 1 and Part 2 are:

- The change from baseline in 4-week overall SBM frequency rate (SBMs/week) during the Study Intervention Period
- The change from baseline in 4-week stool consistency (Bristol Stool Form Scale) reported by LAR/parent/guardian/caregiver during the Study Intervention Period
- The change from baseline in 4-week straining reported by LAR/parent/guardian/caregiver during the Study Intervention Period

The details of the derivation of these efficacy endpoints are provided in [Appendix B](#).

The estimands corresponding to the efficacy endpoints are the mean change from baseline in overall SBM frequency rate, stool consistency, and straining during the study intervention period, regardless of interruption of study drug and without use of rescue medications in the linaclotide and placebo groups in the intent-to-treat (ITT) population.

3.2 Additional Efficacy Endpoints for Part 1 and Part 2

The additional efficacy endpoints for Part 1 and Part 2 are:

- The achievement of no longer meeting modified Rome IV criteria for FC at the end of the 4-week study intervention period
- The global change in symptoms at each week during the study intervention period
- The global severity of symptoms at each week during the study intervention period

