9.0 Efficacy Analyses

9.1 General Considerations

All efficacy analyses will be conducted on the ITT population descriptively for each cohort in Part 1 and by treatment group in Part 2. No statistical testing will be performed in this study. Additionally, if any cohort has the same linaclotide dose as the other cohorts, pooled summaries will also be provided.

Baseline values for efficacy endpoints related to daily eDiary responses will be derived from the eDiary in the preintervention period, specifically the time period from 14 days before enrollment/randomization up to the time of enrollment/randomization in each cohort.

A SBM is a BM that occurs in the absence of laxative, suppository, or enema use on the calendar day of the BM or the calendar day before the BM. Caregiver-observed SBMs are defined as SBMs reported in the eDiary for which the caregiver identified being with the child for.

Baseline SBM weekly rates, stool consistency for caregiver-observed SBMs, and straining for caregiver-observed SBMs will be derived as discussed in [Appendix B](#) from 14 days prior to enrollment/randomization and up to the time of enrollment/randomization. A subject's baseline stool consistency and straining reported for caregiver-observed SBMs cannot be assessed if the subject does not have at least 1 caregiver-observed SBM during the preintervention period. For subjects with no caregiver-observed SBMs reported in the eDiary during a study period, the consistency and straining assessments reported by caregiver will be considered missing for that study period in the analyses. Subjects with

missing baseline consistency and straining reported by the caregiver will be excluded from the respective consistency and straining change from baseline analyses.

Baseline value for the global severity in symptoms will be based on the last non-missing assessment on or before the date of first dose of study intervention.

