The global items consist of two items, one assessing global change in the child's symptoms and one assessing the global severity of the child's symptoms. Both global

items will be completed weekly on the eDiary by the caregiver. The global severity item will be completed beginning at the preintervention period through the study intervention period and the global change item will be completed beginning at one week after Enrollment/Randomization through the study intervention period.

Global Change Item

The global change item assesses the change in the child's constipation (1 item) as follows:

Please choose the response below that best describes the overall change in your child's constipation since he/she started taking the study medication.

- Much better
- A little better
- No change
- A little worse
- Much worse

Global Severity Item

The global severity item assesses the severity of the child's constipation (1 item) as follows:

How would you rate the severity of the child's constipation over the past 7 days?

- None
- Mild
- Moderate
- Severe
- Very severe

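### The global change item is anchored at the start of study medication, so the Cohort 2 and 3 weekly summaries may mix two reference points when children continue from a lower-dose cohort

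*SAP*

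**What the plan says.** SAP Section 3.2 lists as an additional efficacy endpoint: "The global change in symptoms at each week during the study intervention period". SAP Appendix B gives the question. The caregiver picks one of five categories, from much better to much worse, for the "overall change in your child's constipation since he/she started taking the study medication". The wording names no cohort, dose or intervention period. On timing, Appendix B says that the "global change item will be completed beginning at one week after Enrollment/Randomization through the study intervention period".

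In Part 1 a child may take more than one course. Protocol Section 4.1 and SAP Section 2.3 offer children in Cohorts 1 and 2 a place in the next cohort "if their symptoms have not improved at that respective dose" (2 or fewer SBMs per week), provided that the drug was tolerated and the parent or guardian agrees. These children must "repeat all screening procedures and eDiaries if > 30 days have elapsed since the subject's last dose in the previous cohort".

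On analysis, SAP Section 9.1 states: "All efficacy analyses will be conducted on the ITT population descriptively for each cohort in Part 1 and by treatment group in Part 2". It adds pooled summaries where cohorts share a dose. SAP Section 5.0 provides a listing of children enrolled in more than one cohort. No efficacy summary separates them.

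**The concern.** In Part 1 a cohort is a dose, so a cohort row for global change will be read as change on that dose. That reading is right for a newly enrolled child, whose study medication began on Day 1 of the cohort. For a continuing child the drug is the same, treatment is open label, and on the plain words it began in the earlier cohort. The answer then covers the lower-dose course, any gap and the weeks on the current dose.

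The daily eDiary endpoints avoid this because SAP Section 9.1 takes their baseline from a 14-day window "up to the time of enrollment/randomization in each cohort". The global change item carries its reference point inside the question, so a baseline rule cannot reset it. At stake is whether the 18 and 36 µg rows each report one quantity or two under a single label.

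**Working it through.** The documents state no figure for this point, so none can be reproduced. The check is a comparison of text followed by elapsed time.

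**Inputs**
- Course length: 4 weeks per cohort (Protocol Section 4.1).
- Earlier courses possible: 0, 1 or 2 (Cohorts 1 and 2 feed the next cohort, up to Cohort 3).
- Item answered at Weeks 1 to 4 of each course (SAP Section 3.2 and Appendix B).
- Gap between courses: not fixed. I take 0 as the minimum and 30 days (4.3 weeks) as an illustration, since 30 days is the threshold for repeating screening and eDiaries.
- Planned cohort size: 6 (SAP Section 2.3).

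**Span covered by a literal answer**

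Weeks since first study dose = (earlier completed courses) × (4 + gap) + current week.

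| Earlier courses | Gap | Week 1 | Week 4 |
|---|---|---|---|
| 0 | – | 1 | 4 |
| 1 | 0 | 4 + 1 = 5 | 4 + 4 = 8 |
| 2 | 0 | 8 + 1 = 9 | 8 + 4 = 12 |
| 1 | 30 days | 9.3 | 12.3 |
| 2 | 30 days | 17.6 | 20.6 |

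These are elapsed times. They do not estimate how far any category percentage would move.

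**Weight of one continuing child**

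The documents do not say whether continuing children count within the planned six. If they do, one child is 1/6 = 16.7% of the row. If one is added to six new children, the share is 1/7 = 14.3%. The number continuing is not given and could be zero.

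**Where the item could have been re-anchored**
- The timing rule in Appendix B fixes when the question is first asked. It does not fix what the answer is compared with.
- The per-cohort baseline in SAP Section 9.1 is limited to daily eDiary responses, that is, the three key endpoints.
- The carry-over rule in SAP Section 10.1 covers safety baselines only.
- Caregiver training on the eDiary is required (Operations Manual Section 3.7), but its content on this item is not in the documents.

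**Which rows are exposed**
- Cohort 1 is the first course for every child, and Part 2 recruits new subjects. Neither has continuing children.
- Cohorts 2 and 3 can have them.
- A pooled row of Part 1 and Part 2 children at the selected dose can include them if that dose is 18 or 36 µg. At 9 µg it cannot.

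**The case against.** **The literal anchor is not the only possible reading.** A caregiver starting a new course, who first meets the question again one week after enrolment in it, may answer from that start. This stands, and it rules out saying that the item definitely measures change since the lower dose began. With no instruction either way, though, one row may hold both kinds of answer, which is the same difficulty.

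**The continuation rule limits the damage.** Children continue only if they still have 2 or fewer SBMs per week, the same limit as at entry. Where little changed on the lower dose, the two anchors give similar answers. This also stands in part. A reader might infer that the higher dose is credited with the lower dose's effect, but the documents support only that it may be. The rule concerns SBM frequency, while the item rates constipation overall, so other symptoms may have improved or worsened.

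**Weekly trends.** A reader might infer that the Week 1 to Week 4 trends are invalid. They are not, for a caregiver who keeps one anchor: movement within a child still reflects the current course. The level is what becomes hard to interpret.

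**Contrast with the other endpoints.** A reader might infer that every other efficacy endpoint resets by cohort. SAP Section 9.1 says so only for the daily eDiary endpoints. The global severity baseline is tied to the first dose of study intervention without saying in which cohort, and the Rome IV endpoint is an end-of-treatment status with no change from baseline.

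**Small consequence.** The endpoint is additional and descriptive, with no testing. The dose-selection criteria in Protocol Section 4.1 name treatment-related AESIs, SBM frequency and the Bristol scale, not this item. All of this stands and keeps the point minor.

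**Conclusion.** The point holds as a minor one. As written, the Cohort 2 and 3 global change summaries, and any same-dose pooled summary that includes those cohorts, may combine change over 1 to 4 weeks on the current dose with change over at least 5 to 8 weeks after one completed earlier course, or 9 to 12 weeks after two, plus gaps.

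This rests on the literal wording of the item, on completed four-week courses and on at least one child continuing. The effect on the reported percentages cannot be sized from the documents. The ratio of spans at Week 1 (5 to 1, or 9 to 1) should not be read as bias, and the 16.7% share applies only if continuing children count within the six.

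Cohort 1, the randomised Part 2 comparison, the key endpoints and the stated dose-selection criteria are not affected.

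**What to change.** In SAP Section 9.4.1 and Appendix B:

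1. Present the cohort-by-week global change summary for children on their first linaclotide course in the study.
2. Show continuing children's answers separately, labelled as change since first study medication, with a note that some caregivers may have answered from the start of the current course.
3. For description between doses in continuing children, use the weekly global severity score, whose 7-day recall means the same in every cohort. If its change from baseline is used, state in SAP Section 9.1 that the baseline is taken per cohort.

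This is SAP wording only. It needs no eDiary change and no new data. The cost is fewer children in the Cohort 2 and 3 global change rows. Because SAP Section 4.0 uses the ITT Population for all efficacy analyses, an all-ITT row can be kept beside the first-course row with a footnote stating the mixed anchor.
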